12.3 Statistical analysis

12.3.1 Disposition of subjects

Subject disposition will be presented separately for subjects in initial treatment and continuation treatment. For all randomised subjects and for subjects in the continuation treatment analysis set, the reasons for permanent discontinuation of IMP and for leaving the trial in the initial treatment period will be presented by last visit attended and by treatment group.

Trial ID: LP0162-1339	Date: 29-Aug-2018	Version: 4.0
		Page 85 of 129

12.3.2 Demographics and other baseline characteristics

Descriptive statistics of demographics and other baseline characteristics will be presented separately for all randomised subjects and for the continuation treatment analysis set. The presentations will be overall and by treatment group. Presentations of age, sex, ethnicity, race, baseline disease severity, and Worst Daily Pruritus NRS weekly average at baseline will also be given by region and by baseline disease severity (IGA 3 or 4).

Demographics include age, sex, race, and ethnicity. Other baseline characteristics include vital signs (including height, weight, body mass index), duration of AD, concurrent diagnoses (from medical history and indications for concomitant medication), concomitant medication, and previous AD treatments.

12.3.3 Exposure and treatment compliance

12.3.3.1 Exposure

Exposure to treatment will be presented for the safety analysis set (initial treatment) and continuation treatment safety analysis set (continuation treatment) as days of exposure per treatment group.

For the full trial period, the days of exposure on tralokinumab irrespective of treatment group will be summarised - subtracting potential periods on placebo - for the safety analysis set.

12.3.3.2 Treatment compliance

Adherence to treatment regimen will be recorded in the eCRF. The log of drug administration may be used as source. If any complications or deviations in administration are observed, these will be described as protocol deviations.

Adherence will be presented for the safety analysis set (initial treatment) and for the continuation treatment safety analysis set (continuation treatment) for each treatment group.

[figure not shown]
12.3.4 Multiple testing procedure

To control the overall type 1 error rate, the primary analyses of the primary estimands for the primary and secondary endpoints for the initial treatment period will follow the hierarchical testing procedure outlined in Panel 11. The hypothesis relating to a specific endpoint cannot be rejected unless all hypotheses relating to endpoints earlier in the hierarchy are also rejected.

Trial ID: LP0162-1339	Date: 29-Aug-2018	Version: 4.0
		Page 86 of 129

Panel 11 Testing procedure for primary and secondary endpoints

 $Arrows \, indicate \, order \, of \, testing \, when \, superiority \, is \, shown \, for \, an \, endpoint \, within \, a \, box.$

Abbreviations: DLQI, Dermatology Life Quality Index; EASI75, at least 75% reduction in Eczema Area and Severity Index score; IGA, Investigator's Global Assessment.

The procedure will be as follows:

IGA 0/1 at Week 16 between tralokinumab+TCS and placebo+TCS will be evaluated at a 5% significance level. If the test is significant, EASI75 at Week 16 between tralokinumab+TCS and placebo+TCS will be evaluated at a 5% significance level.

If both these tests are significant, the 5% significance level (alpha) will be propagated to the three secondary endpoints: SCORAD at Week 16, Pruritus at Week 16, and DLQI at Week 16. The evaluations of the three secondary endpoints between tralokinumab+TCS and placebo+TCS will use the Holm method (35) for 3 ordered p-values at a 5% significance level to adjust for multiplicity.

12.3.5 Analysis of primary endpoints

Three estimands addressing different aspects of the trial objectives will be defined:

- Primary estimand: 'composite'.
- Secondary estimand: 'hypothetical'.
- Tertiary estimand: 'treatment policy'.

Trial ID: LP0162-1339	Date: 29-Aug-2018	Version: 4.0
		Page 87 of 129

The applied estimands incorporate two main types of events that influence how the treatment effects are estimated:

- **Initiation of rescue medication**: Some of the estimands use the initiation of rescue medication as an event that modifies the applied value of an endpoint, e.g. by defining a subject receiving rescue medication as a non-responder.
- **Permanent discontinuation of IMP**: This event occurs when a subject is permanently withdrawn from the treatment or the trial as described in section 8.5. This can either happen at his/her own initiative or at the investigator's discretion. The event also includes the possibility of a subject being lost to follow-up. The timing of the event is defined as the date of the early termination visit for withdrawn subjects or in the case of a subject lost to follow-up the date of the last known visit to the clinic. As for the rescue medication, the event type is used to modify an applied endpoint value.

All analyses will be based on the full analysis set unless otherwise specified.

12.3.5.1 Primary estimand: 'composite'

The primary estimand for the primary endpoints will be:

• Treatment difference in response rates of IGA 0/1 and EASI75 after 16 weeks achieved without rescue medication, regardless of treatment discontinuation.

The primary estimand assesses the expected difference in response rates (defined as response obtained without initiation of any rescue medication) after 16 weeks, resulting from initiation of a treatment regimen with tralokinumab+TCS compared to a treatment regimen with placebo+TCS.

Primary analysis for the primary estimand

Data retrieved at Week 16 for subjects who have permanently discontinued IMP prior to Week 16 will be included in the analysis. Subjects who prior to the Week 16 visit have received rescue medication will be considered non-responders, reflecting an assumption that initiation of rescue medication indicates failure of the randomised treatment to achieve response, and that a (possible) observed positive response after initiation of rescue medication is not attributable to the randomised treatment. Missing data for subjects who do not attend the Week 16 visit and where rescue medication has not been used prior to Week 16, will be imputed as non-responders.

The difference in response rates between treatment groups will be analysed using the Cochran-Mantel-Haenszel test stratified by region (Europe and North America) and baseline

Trial ID: LP0162-1339	Date: 29-Aug-2018	Version: 4.0
		Page 88 of 129

disease severity (IGA 3 or 4). The treatment estimate and the corresponding 95% CI will be presented. The null hypothesis of no difference in response rates between tralokinumab+TCS and placebo+TCS will be tested against the 2-sided alternative that there is a difference.

The primary endpoints will be tested sequentially at a 5% significance level. IGA 0/1 will be tested first, and, if significant, then EASI75 will be tested. If both primary null hypotheses are rejected, the secondary endpoints will be tested.

Sensitivity analyses for the primary estimand

Two sensitivity analyses are specified for the primary estimand. In both cases the same Cochran-Mantel-Haenszel test as used for the primary analysis will be applied including stratification by region and baseline disease severity.

The purpose of the analyses is to assess the robustness of results of the primary analysis with respect to the retrieved data at Week 16 and assumptions regarding missing Week 16 data.

Sensitivity analysis 1: All subjects who have permanently discontinued IMP prior to Week 16 will be imputed as non-responders, even if no rescue medication has been used. This is to reflect a situation where retrieved efficacy data and concomitant medications could be registered less accurately for subjects who have discontinued treatment.

Sensitivity analysis 2: Rather than imputing all subjects who do not attend the Week 16 visit and where rescue medication has not been used as non-responders, the following approach will be applied. If subjects have withdrawn due to an AE or due to lack of efficacy, they are still considered non-responders. Data missing for other reasons will be imputed using last observation carried forward (LOCF), hereby assuming that the last value is a more reliable estimate of the missing response (than a non-response).

Supplementary analysis

The primary analysis of the primary estimand is repeated based on the per protocol analysis set.

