8.5 Discontinuation

A subject may withdraw from trial or from treatment at any time (prior to first dose or during the treatment period) at his/her own request. A subject may be withdrawn at any time at the discretion of the investigator. Discontinued subjects will not be replaced.

Medical reasons for permanent discontinuation of IMP are given in Section 9.7.1.

Trial ID: LP0162-1339	Date: 29-Aug-2018	Version: 4.0
		Page 45 of 129

Subjects who permanently discontinue IMP for any reason will be asked to attend an early termination visit and return to the trial site for 1 or 2 additional visits as indicated below depending on the time of discontinuation of IMP (see the schedule of procedures [Panel 3] for data to be collected at these visits). The investigator will review any AEs which will be followed-up according to Section 11.6, if the subject agrees.

Subjects who permanently discontinue IMP prior to Week 16 will be asked to attend:

- Early termination visit.
- Nominal Week 16 visit (16 weeks after randomisation).
- Safety follow-up visit (16 weeks after last administration of IMP).

Subjects who permanently discontinue IMP at Week 16 or after Week 16 will be asked to attend:

- Early termination visit.
- Safety follow-up visit (16 weeks after last administration of IMP).

If a subject withdraws from the trial, he/she may request destruction of any samples taken and not tested, and the investigator must document this in the site's trial records.

Reason(s) for discontinuation from IMP and withdrawal from the trial must be recorded in the medical records and the eCRF (lack of efficacy, AE, withdrawal by subject, lost to follow-up, death, other). For subjects randomised to IMP but not attending any post-baseline visits, it will be recorded whether any safety evaluations were performed after exposure to IMP.

Lost to follow-up

A subject will be considered lost to follow-up if they repeatedly fail to return for scheduled visits and if the trial site is not able to get in contact with the subject.

Trial ID: LP0162-1339	Date: 29-Aug-2018	Version: 4.0
		Page 46 of 129

The following actions must be taken if a subject fails to return to the trial site for a required visit:

- The trial site must attempt to contact the subject and reschedule the missed visit as soon as possible and counsel the subject on the importance of maintaining the assigned visit schedule and ascertain whether the subject wishes to and/or should continue in the trial.

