12.1 Sample size

A total of 369 subjects will be randomised 2:1 to initial treatment in this trial (246 subjects in the tralokinumab+TCS arm; 123 subjects in the placebo+TCS arm).

The primary endpoints for initial treatment, IGA 0/1 and EASI75 at Week 16, are to be evaluated hierarchically testing both hypotheses of no difference between active and placebo at the 5% significance level. The hypothesis for IGA 0/1 will be tested first; if significant, the EASI75 hypothesis will be tested.

The null hypothesis for the first primary endpoint is that there is no difference at Week 16 in obtaining IGA 0/1 between tralokinumab+TCS and placebo+TCS. The null hypothesis for the second primary endpoint is that there is no difference at Week 16 in obtaining EASI75 between tralokinumab+TCS and placebo+TCS. Each hypothesis will be tested against the 2-sided alternative that there is a difference between the 2 treatment groups.

For the single endpoint IGA 0/1 at Week 16, a sample size of 369 subjects randomised 2:1 will provide 90% power to detect a difference between the 2 arms, assuming response rates of 30% for tralokinumab+TCS and 15% for placebo+TCS. For the single endpoint EASI75 at Week 16, a sample size of 369 will provide a nominal power >99.9% to detect a difference between tralokinumab+TCS and placebo+TCS, assuming EASI75 response rates of 40% and 15%, respectively. The combined power for demonstrating a significant difference for both endpoints is therefore effectively also 90% with a sample size of 369 subjects, even when assuming no correlation between the 2 primary endpoints. In all cases, the evaluations will be made with a 2-sided 5% significance level.

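### As written, sensitivity analysis 2 of the primary estimand carries a death forward and can score it as a Week 16 response, and it does not say whose withdrawal reason counts

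*Protocol*

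**What the plan says.** In the primary analysis of the primary estimand (Section 12.3.5.1), every subject who misses the Week 16 visit without earlier rescue is a non-responder. Rescued subjects are non-responders in any case.

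The section then names two sensitivity analyses, both using the same stratified Cochran-Mantel-Haenszel test. Their purpose is to check robustness to the data retrieved after IMP discontinuation and to the assumptions about missing Week 16 data.

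- Sensitivity analysis 1 sets every subject who permanently stopped IMP before Week 16 to non-response.
- Sensitivity analysis 2 concerns subjects with no Week 16 visit and no rescue. For them: "If subjects have withdrawn due to an AE or due to lack of efficacy, they are still considered non-responders". And: "Data missing for other reasons will be imputed using last observation carried forward (LOCF", on the ground that the last value is the more reliable guess.

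Section 8.5 says that the reasons for stopping IMP and for leaving the trial are both recorded, from this list: "lack of efficacy, AE, withdrawal by subject, lost to follow-up, death, other".

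**The concern.** The rule in sensitivity analysis 2 works on the recorded reason. It protects two of the six reasons in Section 8.5 and sends the other four to LOCF. Death is one of the four. The rationale given for LOCF cannot apply to someone who has died, yet no exception is made.

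There is a second gap. Two reasons can exist for one subject, one for stopping IMP and one for leaving the trial, and the rule does not say which one governs. A subject whose IMP was stopped for an AE and who was later lost to follow-up could be sorted either way.

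At stake is the credibility of one supportive analysis. A reader of the trial report who found a death counted as a treatment success, or a coding choice settled after unblinding, would discount it.

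**Working it through.** **1. The reasons against the rule** (missing Week 16 data, no rescue)

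| Recorded reason (Section 8.5) | Sensitivity analysis 2 as written |
|---|---|
| Lack of efficacy | non-responder |
| AE | non-responder |
| Withdrawal by subject | LOCF |
| Lost to follow-up | LOCF |
| Death | LOCF |
| Other | LOCF |

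Appendix 2 does have a fatal outcome category, but it classifies the outcome of an AE. It is not the discontinuation or withdrawal reason on which the rule operates.

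**2. What each sensitivity analysis varies.** Discontinued subjects with no Week 16 data are already non-responders in the primary analysis, so sensitivity analysis 1 changes only the retrieved data. Sensitivity analysis 2 is the only one that varies the missing-data assumption, and it does so through a single LOCF scenario.

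**3. Planning figures** (Section 12.1). Inputs: "246 subjects in the tralokinumab+TCS arm; 123 subjects in the placebo+TCS arm"; "assuming response rates of 30% for tralokinumab+TCS and 15% for placebo+TCS"; "the evaluations will be made with a 2-sided 5% significance level". The stated power is reproduced first, by the normal approximation with pooled variance under the null:

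- Pooled rate: (246×0.30 + 123×0.15)/369 = 0.25.
- SE under the null: √[0.25×0.75×(1/246+1/123)] = 0.0478.
- SE under the alternative: √[0.15×0.85/123 + 0.30×0.70/246] = 0.0435.
- Power: Φ[(0.15 − 1.96×0.0478)/0.0435] = 90.2%, against the stated 90%.

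The point does not disturb the sample size.

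**4. Size of one misclassified subject.** The planned counts are 0.30×246 ≈ 74 and 0.15×123 ≈ 18. The unstratified pooled z-test stands in for the stratified test: z = (difference in rates)/√[p(1−p)(1/246+1/123)], with p the pooled rate.

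- 74/246 v 18/123: difference 15.4 points, p = 0.0012.
- One, two or three tralokinumab subjects carried forward as responders (75, 76, 77 of 246): difference 15.9, 16.3, 16.7 points. Each adds 1/246 = 0.41 points.
- One placebo subject carried forward as a responder moves that arm by 1/123 = 0.81 points, and narrows the difference.

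The protocol gives no expected number of deaths. One to three is an assumption for illustration.

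**5. What an arm-specific table would show for IGA 0/1.** Start from the same counts, with k missing placebo subjects and j missing tralokinumab subjects turned into responders:

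| k | j | Counts | p |
|---|---|---|---|
| 6 | 0 | 74/246 v 24/123 | 0.030 |
| 7 | 0 | 74/246 v 25/123 | 0.046 |
| 8 | 0 | 74/246 v 26/123 | 0.068 |
| 8 | 1 | 75/246 v 26/123 | 0.058 |
| 8 | 2 | 76/246 v 26/123 | 0.048 |

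The protocol gives no missing-data rate either. If 5% of placebo subjects were missing (6 subjects), significance could not be lost. At 10%, 15% or 20% missing, with j = 0, it would be lost at 8 of 12, 8 of 18 or 8 of 25.

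For EASI75 ("assuming EASI75 response rates of 40% and 15%, respectively", so 98/246 v 18/123) it takes k = 19: 98/246 v 37/123 gives p = 0.067, and k = 18 gives 0.047.

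**The case against.** The strongest reply is that nothing confirmatory rests on this. The primary analysis counts all Week 16 non-attenders as failures. Sensitivity analysis 1 counts all permanent discontinuers as failures. Sensitivity analysis 2 is a deliberate relaxation that supports no claim alone. This stands, and it limits the size of the point.

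On death, a site might code a fatal event as withdrawal for an AE, and the case also needs a death before Week 16, without rescue, in a subject last seen as a responder. That makes it rare. But the list offers death as its own reason, so the outcome would turn on which box a site ticks.

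On AE-driven dropout, a reader might infer that a subject who stopped IMP for an AE and was then lost to follow-up is certainly carried forward. The text does not go that far. Section 12.3.5 defines permanent discontinuation as covering withdrawal from treatment as well as from the trial, so withdrawal due to an AE can fairly be read to include IMP stopped for an AE. What remains is an ambiguity.

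A reader might also infer that the sensitivity analyses fail their stated purpose because they apply one rule to both arms. They do not: sensitivity analysis 1 varies the retrieved data, sensitivity analysis 2 varies the missing data, and LOCF can yield different response rates by arm. The protocol never undertakes to find a tipping point, and such tables are commonly left to the SAP. Section 12.3.5.2 also plans copy-reference imputation of both primary endpoints, although for the hypothetical estimand, which discards data after IMP discontinuation or rescue.

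Last, it is tempting to say that 6.5% missing placebo data (8 of 123) could overturn IGA 0/1. That requires all 8 to be responders, when the planned 15% rate would give about 1 (0.15×8 = 1.2), and missing tralokinumab subjects to stay failures. Two tralokinumab responders restore significance.

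**Conclusion.** The rule is wrong as written for death and incomplete on which recorded reason governs. The effect is small: about 0.4 percentage points per tralokinumab subject and 0.8 per placebo subject, in one supportive analysis, in either direction. The primary analysis, sensitivity analysis 1, the sample size and the power are unaffected.

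This conclusion rests on reading the rule against the reason list in Section 8.5. The counts in the illustrations assume that the planning rates are met exactly and use an unstratified test.

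The documents do not support a claim that the primary result is exposed. At the planning rates, IGA 0/1 loses significance only in an extreme corner: at least 8 missing placebo subjects respond and almost no missing tralokinumab subject does.

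**What to change.** Add to sensitivity analysis 2: among subjects with missing Week 16 data and no rescue, those who died, and those who stopped IMP or left the trial because of an AE or lack of efficacy (either recorded reason suffices), are non-responders; LOCF applies to the rest. Limiting this to missing Week 16 data leaves the handling of retrieved data as planned.

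Optionally, supplement LOCF, without replacing it, with a two-way tipping-point table: the number of missing subjects counted as responders in each arm, with the same Cochran-Mantel-Haenszel test.

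The cost is one sentence and, if the option is taken, one table. Both reasons are already collected, so no new data are needed. Section 12.3.12 provides for an SAP update finalised before the randomisation code is broken, which is the place and the time to settle this. The fix could move the sensitivity result either way, since it can remove carried-forward responders from both arms.

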12.3.5.2 Secondary estimand: 'hypothetical'

The secondary estimand for the primary endpoints will be:

Trial ID: LP0162-1339	Date: 29-Aug-2018	Version: 4.0
		Page 89 of 129

Treatment difference in response rates of IGA 0/1 and EASI75 after 16 weeks
if all subjects adhered to the treatment regimen in the sense that they did not
discontinue IMP permanently and no rescue medication was made available
before Week 16.

The secondary estimand assesses the expected difference in response rates achieved when adhering to the treatment regimen tralokinumab+TCS with no rescue medication as compared to a treatment regimen with placebo+TCS with no rescue medication.

Primary analysis of the secondary estimand

Data collected after permanent discontinuation of IMP or after initiation of rescue medication will not be applied in the analysis.

IGA 0/1 responder imputation

Imputation of missing binary IGA 0/1 data at Week 16 will be done using multiple imputations of the underlying 5-point IGA values within the 2 groups defined according to randomised treatment arm assuming that data is missing at random within each arm.

- 1. In each group, intermittent missing values will be imputed using LOCF to obtain a monotone missing data pattern.
- 2. An ordinal logistic regression model assuming proportional odds will be fitted to the IGA value at Week 2. The model will include effects of region, and baseline disease severity (IGA 3 or 4) as factors. The estimated parameters, and their variances, will be used to impute missing IGA values at Week 2. 100 copies of the dataset will be generated (seed=111099).
- 3. For each of the 100 copies of the dataset, missing values at Week 4 will be imputed in the same way as for Week 2. The imputations will be based on a proportional odds logistic regression model with effects of region and baseline disease severity (IGA 3 or 4) together with the IGA value at Week 2 as factors. The estimated parameters, and their variances, will be used to impute missing values at Week 4.
- 4. This stepwise procedure will then be repeated sequentially for Week 6, 8, 10, 12, 14, and 16 with the modification that only the IGA values from the two preceding visits will be included as factors in addition to region and baseline disease severity. The missing binary IGA 0/1 response at Week 16 will be derived from the corresponding underlying imputed IGA value.

Trial ID: LP0162-1339	Date: 29-Aug-2018	Version: 4.0
		Page 90 of 129

EASI75 responder imputation

Imputation of missing binary EASI75 data at Week 16 will be done using multiple imputations of the underlying 72-point EASI values within the two groups defined according to randomised treatment arm assuming that data is missing at random within each arm.

- 1. Intermittent missing values will be imputed in each group using a Markov Chain Monte Carlo method to obtain a monotone missing data pattern and 100 copies of the dataset will be generated (seed=290997).
- 2. An ANCOVA model is fitted to the EASI value at Week 2. The model will include effects of baseline EASI as a covariate, and region, and baseline disease severity (IGA 3 or 4) as factors. The estimated parameters, and their variances, will be used to impute missing EASI values at Week 2. 100 copies of the dataset will be generated (seed=111099).
- 3. For each of the 100 copies of the dataset, missing EASI values at Week 4 will be imputed in the same way as for Week 2. The imputations will be based on the same ANCOVA model with effects of baseline EASI as a covariate, and region, and baseline disease severity (IGA 3 or 4) as factors together with the EASI value at Week 2 as covariate. The estimated parameters, and their variances, will be used to impute missing values at Week 4.
- 4. This stepwise procedure will then be repeated sequentially for Week 6, 8, 10, 12, 14, and 16 with the modification that only the EASI values from the preceding two visits will be included as covariates in addition to baseline EASI as a covariate, and region and baseline disease severity as factors. The missing binary EASI75 response at Week 16 will be derived from the corresponding underlying imputed EASI value.

Analysis of Week 16 response

For each of the 100 complete data sets, the difference in response rates (either the IGA 0/1 or the EASI75) between treatment groups will be analysed using the Cochran-Mantel-Haenszel test stratified by region (Europe and North America) and baseline disease severity (IGA 3 or 4). The estimates and standard errors from the 100 analyses will be pooled to one estimated treatment difference and associated standard error using Rubin's rule to draw inference. From these pooled estimates, the 95% CI for the treatment difference will be calculated.

Sensitivity analysis for the secondary estimand

Rather than assuming that observations are missing at random within each treatment arm, it is assumed that missing data from subjects who discontinue IMP permanently/receive rescue medication in the tralokinumab+TCS arm will resemble missing data from subjects from the

Trial ID: LP0162-1339	Date: 29-Aug-2018	Version: 4.0
		Page 91 of 129

placebo arm who do not discontinue IMP permanently/receive rescue medication. The underlying assumption is that the effect of tralokinumab following rescue medication or permanent treatment discontinuation is similar to the effect of placebo. It should be noticed that this assumption is pronouncedly conservative in favour of placebo as it tends to minimise the differences between arms.

Imputation of missing data at Week 16 will be done using a pattern mixture model where missing data in the tralokinumab+TCS arm as well as the placebo+TCS arm will be imputed from observed data in the placebo+TCS arm (using a so-called copy-reference approach). With this exemption, the stepwise multiple imputation procedure and subsequent analysis will be conducted in the same way as specified for the primary analysis of the secondary estimand.

